Biomarkers and antithrombotic treatment in cervical artery dissection
The TREAT-CAD trial

ClinicalTrials.gov Identifier: NCT 02046460

Statistical analysis plan – dated Dec. 18th 2019

[name]. [name]
Universitätsspital Basel
Neurologie
[name]
[name]

Basel, December 18, 2019

Methods & Statistics

Study Title	Biomarkers and antithrombotic treatment in cervical artery dissection
Internal DKF ID	[name]
Document Status	Confirmed Final Report

This statistical report and analysis plan will be finalized before database closure and will be under version control at the Clinical Trial Unit, University Hospital Basel.

1 Background

Antithrombotic treatment in cervical artery dissection (CAD) is still a matter of debate. Most physicians prescribe anticoagulants for stroke prevention in CAD-patients although this approach is not evidence-based.

This randomized controlled, open labeled multicenter non-inferiority trial with blinded assessment of outcome events compares anticoagulant treatment to antiplatelet treatment.

2 Analysis data sets

The **full analysis set (FAS)** consists of all patients that were randomized. According to the intention-to-treat principle, each patient will be analyzed according to the treatment she/he was randomly allocated to. Patients who withdrew their consent during the course of the study will be analyzed in the FAS including only their baseline data.

The **per protocol set (PP)** consists of patients in the FAS set without any of the following major protocol deviation:

- no dissection: diagnostic criteria for CAD not met in central MR reading
- violation of an inclusion criterion or having an exclusion criterion (for pregnancy, only a positive pregnancy test will be considered as a major protocol deviation)¹
- switching between treatment groups (cross-over) or discontinuation of the allocated treatment before follow-up visit 2 for any reason other than as a reaction to a primary outcome-event or an SAE
- MRI at follow-up visit 1 earlier or later than 14 +/- 10 days
- follow-up visit 2 prior to 60 days after randomization ²

The following deviations will be considered as minor protocol deviations:

- result of pregnancy test too late but negative (ie. confirmed absence of pregnancy after inclusion and randomization)
- randomization or start of treatment allocated not within 72h after initial MRI scan
- changes in treatments within the allocated treatment arm (eg. dosage of ASA 100mg rather than 300 mg) prior to follow-up visit 2

Patients with only minor protocol deviations will still be part of the PP.

Each patient will be analyzed according to the treatment she/he received until follow-up visit 2.

3 Demographic and baseline characteristics

Demographics and relevant baseline variables will be summarized for the PP and the FAS set. All summaries will be broken down by the treatment patients received.

Categorical data will be presented as frequencies and percentages. For continuous variables, the total number of measurements as well as the mean and the standard deviation will be presented. For skewed data the median and the lower and upper quartile will be shown.

4 Primary objective

The primary objective is to demonstrate the non-inferiority of anti-platelet treatment to anti-coagulant treatment in preventing further cerebrovascular ischemic events in patients with cervical artery dissection (CAD).

¹The protocol does not distinguish between “confirmed absence of pregnancy” and “assumed but unconfirmed absence of pregnancy”. We only consider the latter as a major protocol deviation since patients with a late but negative pregnancy test are still part of the intended study population.

²In the protocol the window for visit 2 was 90 +/-30 days.

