4.1 Primary endpoint

The primary endpoint - **Cerebrovascular Ischemia**, major **Hemorrhagic events** or **Death (CIHD)** - is a composite endpoint. It is defined as the occurrence of at least one of the following events during the treatment period:

1. Cerebral ischemic events (clinical) or surrogate findings for cerebral ischemia:
 - (a) Any ischemic stroke, defined as: new symptomatic neurologic deterioration lasting at least 24 hours that was not attributable to a non-ischemic cause, or a new symptomatic neurologic deterioration that was not attributable to a non-ischemic cause and was accompanied by neuroimaging evidence of a new brain infarction. ([Amarenco et al. \(2018\)](#)). This includes Transient Ischemic Attack (TIA) with Diffusion Weighted Imaging (DWI) lesion. Ischemic stroke also includes retinal infarction defined according to ([Hayreh & Zimmerman \(2005\)](#))
 - (b) New acute ischemic lesions on DWI MRI since baseline are defined as: (1) those with an unequivocal lack of continuity between new and existing (on baseline imaging) lesions on the same slice as well as on adjacent slices – irrespective of vascular territories and lesion pattern, ([Gensicke et al. \(2015\)](#)) and (2) “acute” being defined as a hyperintense signal alteration on DWI with a corresponding hypointense or isointense signal on ADC (Apparent Diffusion Coefficient) maps ([Gensicke et al. \(2015\)](#)).
2. Hemorrhages (clinical) or surrogate findings:
 - (a) any major extracranial hemorrhage: any clinically apparent extracranial bleeding requiring any kind of intervention [including hospitalization or prolongation of hospitalization] or leading to death.
 - (b) any symptomatic intracranial hemorrhage defined as: any documented intracranial hemorrhage - i.e. an acute extravasation of blood into the brain parenchyma ([Amarenco et al. \(2018\)](#)) - that was temporally related to any deterioration in the patient’s clinical condition.
 - (c) any new, asymptomatic micro- or macrobleeds (visible on follow-up brain T2*-MRI or Susceptibility weighted imaging (SWI), which were absent on the baseline MR-scan) defined as: (1) those with an unequivocal lack of continuity between new and existing (on baseline imaging) lesions on the same slice as well as on adjacent slices – irrespective of vascular territories and lesion pattern, ([Gensicke et al. \(2015\)](#)) and lesions being defined as hypointense brain lesions with clear margins on T2*-MRI or SWI.

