4.5 Supportive analyses and sensitivity analyses

The following supportive and sensitivity analyses will be conducted to support the main analysis described above (Section 4.3). The rationale for each sensitivity analysis is indicated in bold. All sensitivity analyses except for the sensitivity analysis nr 2 will be performed on the PP. Missing values will be handled as described in section 5.2 if not defined otherwise.

1. **Missing values:** In case of missing values for the primary endpoint, the main analysis will be repeated performing the following imputations

³In the protocol, this was planned as sensitivity analysis. However, given the rather young patient population, we do not expect preexisting micro- or macrobleeds. Therefore the probability of falsely labeling an existing microbleed as new due to missing baseline T2* - or SWI MRI was considered to be small and the aim to preserve the randomization was of overriding importance. Therefore the two analyses were switched.

- (a) Missing values in the primary endpoint will be imputed as CIHD events (assuming the worst for patients without follow-up).
 - (b) Missing values in the primary endpoint will be imputed as no CIHD events (assuming the best for patients without follow-up).
2. **Choice of analysis population (PP vs. FAS):** The analysis will be repeated on the FAS and compared to the main analysis. According to the intention-to-treat principle, each patient will be analyzed according to the treatment she/he was randomly allocated to. In case of missing values for the primary endpoint, the following imputations will be performed:
 - (a) Missing values in the primary endpoint will be imputed as CIHD events (assuming the worst for patients without follow-up).
 - (b) Missing values in the primary endpoint will be imputed as no CIHD events (assuming the best for patients without follow-up).
 - (c) Patients with missing values in the primary endpoint will be excluded from the analysis. Inverse probability of censoring weights will be used as described for the main analysis in section 5.2.
3. **Incomplete information about micro- or macrobleeds at baseline:** The main analysis will be repeated excluding patients without baseline information with regards to micro- or macrobleeds.

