5.2 Missing values

Primary endpoint In patients with missing information on micro- or macrobleeds at baseline, any lesion detected on follow-up T2*- or SWI MRI will be considered as new lesion (section 4.1 and sensitivity analysis 3). For missing values in the primary endpoint (e.g. due to missing follow-up), inverse probability of censoring weights will be estimated. Thereby stabilized inverse probability of weights for missingness of the primary endpoint will be estimated for each treatment arm according to (Robins et al., 2000) and (Hernan & Robins, 2006; Austin & Stuart, 2015). The weights will be estimated on the PP except for the sensitivity analysis 2, where the FAS will be used. The following variables will be used to estimate the weights: age, sex, occlusion of dissected artery, and National Institutes of Health Stroke Scale (NIHSS). If the patient did not have a stroke, 0 will be imputed for the NIHSS. Missing values will be further investigated in sensitivity analyses (see sensitivity analysis 1).

Covariates Missing values in covariates used to estimate the inverse probability of censoring weights will be imputed. If the number of missing values does not exceed 5% in each variable of interest the median (continuous variables) or the mode (= most frequent category, categorical variables) will be used. If there is one covariate with more than 5% missing values, 5 multiple imputations will be done as described in van Buuren & Groothuis-Oudshoorn (2011). To this end we will generate 5 imputed data sets. In a second step we will estimate the weights for each imputed data set. Thereafter, we will stabilize and average the weights over the 5 imputations. In case of severe variability of the stabilized weights between imputations, we will increase number of imputations. Thereby the weights will be considered to have "severe variability between imputations" if for any patient the inter-weight variability divided by the number of imputations (the amount the variance would be increased in order to correct for the uncertainty of the imputations when using Rubin's rule, Barnard & Rubin (1999)) is larger than 0.01.

Secondary endpoints: The number of missing values will be presented. No imputations will be performed. Secondary analyses will be complete case analyses.

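### Keeping only baseline data after consent withdrawal turns a primary endpoint event already observed into a missing value in the FAS analysis, and possibly in the primary analysis

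*SAP*

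**What the plan says.** Section 2 puts every randomized patient in the FAS and adds: "Patients who withdrew their consent during the course of the study will be analyzed in the FAS including only their baseline data". It makes no exception for an endpoint event recorded before the withdrawal, and no other section restores one.

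Section 4.1 defines the composite primary endpoint (CIHD): "It is defined as the occurrence of at least one of the following events during the treatment period".

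Section 4.5, sensitivity analysis 2, repeats the analysis on the FAS with three treatments of a missing endpoint:

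- 2a: "Missing values in the primary endpoint will be imputed as CIHD events (assuming the worst for patients without follow-up".
- 2b: "Missing values in the primary endpoint will be imputed as no CIHD events".
- 2c: "Patients with missing values in the primary endpoint will be excluded from the analysis. Inverse probability of censoring weights will be used".

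Section 5.2 estimates those weights, separately by arm, from four variables: age, sex, occlusion of the dissected artery and NIHSS.

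The primary analysis (section 4.3) is on the PP, which section 2 draws from the FAS. Consent withdrawal is not among the major deviations listed there. Stopping the allocated treatment before visit 2 is listed, but not when it is a reaction to a primary event or an SAE. A missing primary endpoint in the PP is handled by the weights of section 5.2.

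**The concern.** For an endpoint of this kind, follow-up after the first qualifying event cannot change the result. A patient who had a stroke or a major bleed and later withdrew has a known outcome. The baseline-only rule makes it unknown, and the plan then fills the gap with an assumption or a weight.

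This matters if withdrawal is related to the event. The trial is open label, so a patient may withdraw because of an event, and the frequency may differ by arm. The values made missing would then be mostly events. In a non-inferiority comparison, events lost from the antiplatelet arm favour the conclusion the trial sets out to show. The FAS analysis is the stated check on the PP result, and two of its three versions would carry this error.

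**Working it through.** **Step 1: trace one patient.** Take a patient with a qualifying event who later withdraws consent.

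| Handling | Counted as | Agrees with what was observed? |
|---|---|---|
| Data up to withdrawal used | event | yes |
| 2a | event | yes, but patients with a missing endpoint and no event are also scored as events |
| 2b | no event | no |
| 2c | removed, others reweighted | the event is lost |

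The weights in 2c remove the bias only if, within arm and given the four covariates, missingness is unrelated to the outcome. Withdrawal caused by an event breaks that condition, and the event is not in the weight model.

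**Step 2: does it reach the primary analysis?** The sentence in section 2 names the FAS. A withdrawn patient may leave the PP through another criterion: treatment stopped before visit 2 for a non-exempt reason, a visit 1 MRI outside 14 ± 10 days, or visit 2 before day 60. A patient who stopped treatment because of a primary event is exempt from the first of these and may remain. If the baseline-only rule follows that patient into the PP, section 5.2 handles the endpoint as in 2c. The SAP does not say whether it does.

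**Step 3: size.** The SAP states no sample size, event rate or number of withdrawals, so there is no figure of its own to reproduce. From the SAP: margin 12 points (section 4.2), and a two-sided 95 % Newcombe interval from continuity-corrected Wilson limits (section 4.3). Assumed: 97 per arm, the event counts below, and weights equal to 1. Differences are antiplatelet minus anticoagulant, so non-inferiority needs an upper limit below 12.

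For x events in n patients, with p = x/n, q = 1 − p, z = 1.96:

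- L = [2np + z² − 1 − z√(z² − 2 − 1/n + 4p(nq + 1))] / [2(n + z²)]
- U = [2np + z² + 1 + z√(z² + 2 − 1/n + 4p(nq − 1))] / [2(n + z²)]
- Upper limit of the difference d = p₁ − p₂: d + √[(U₁ − p₁)² + (p₂ − L₂)²]

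In per cent, 16/97 gives p₁ = 16.49 and U₁ = 25.71; 14/97 gives p₂ = 14.43 and L₂ = 8.40. Hence d = 2.06, and the upper limit is 2.06 + √(9.22² + 6.03²), or 13.07 from unrounded values. With the two patients dropped, 14/95 gives p₁ = 14.74 and U₁ = 23.83. Then d = 0.30, and the upper limit is 0.30 + √(9.09² + 6.03²), or 11.22 from unrounded values.

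| Withdrawals after an event | Upper limit, events used | Patient dropped (as 2c) | Scored as no event (as 2b) |
|---|---|---|---|
| Two, antiplatelet | 16/97 vs 14/97: 13.07 | 14/95 vs 14/97: 11.22 | 14/97 vs 14/97: 10.78 |
| One, antiplatelet | 15/97 vs 14/97: 11.93 | 14/96 vs 14/97: 11.00 | 14/97 vs 14/97: 10.78 |
| One in each arm | 15/97 vs 15/97: 11.03 | 14/96 vs 14/96: 10.88 | 14/97 vs 14/97: 10.78 |
| Two, anticoagulant | 14/97 vs 16/97: 8.98 | 14/97 vs 14/95: 10.55 | 14/97 vs 14/97: 10.78 |

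Only the first row crosses the margin. Keep that pattern (97 per arm, two more antiplatelet events than anticoagulant, both extra patients dropped) and vary the anticoagulant count. The verdict changes for 10 to 17 anticoagulant events. With 6 to 9 both limits are below 12; with 18 to 23 both are above.

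**Step 4: other arm sizes.** Three antiplatelet withdrawals after an event, with 20 % events in each arm when all are used:

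| Per arm | Events used | As 2c | As 2b |
|---|---|---|---|
| 50 | 17.0 | 11.8 | 10.4 |
| 100 | 11.8 | 9.2 | 8.5 |
| 200 | 8.2 | 6.9 | 6.6 |

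**The case against.** The best defence is that the use of data after consent withdrawal is normally settled by the consent form, the ethics approval and the protocol. The protocol is not shown, and the rule may simply carry out what patients agreed to. This stands. The SAP's silence on the reason is no fault in itself, and any change has to be limited by consent.

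It is also fair that the plan partly covers the problem. Analysis 2a, and 1a in the PP, count such a patient as an event, and showing 2a, 2b and 2c together displays how far the result depends on missing endpoints. This is partial cover only. 2a also adds events for patients who had none, so none of the three versions reproduces what was observed.

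Three stronger readings are tempting, and the SAP does not support them:

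- *That the rule contradicts intention to treat.* Section 2 puts the principle this way: "According to the intention-to-treat principle, each patient will be analyzed according to the treatment she/he was randomly allocated to". Withdrawn patients stay in the FAS and in their allocated arm, and 2a and 2b keep them in the denominator. The fault is in the handling of missing data.
- *That the primary analysis is certainly affected because the PP is a subset of the FAS.* The sentence is confined to the FAS, and some withdrawn patients would leave the PP on other criteria.
- *That two unused events reverse the verdict.* This needs both in the antiplatelet arm and a result already near the margin.

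Nor does the SAP say that records are erased. It limits what is analyzed.

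**Conclusion.** The point holds within these limits. The rule, as written, makes a known primary endpoint missing for any patient who had an event and then withdrew consent. In the FAS analysis, 2b then misstates that outcome and 2c loses it, with weights that cannot repair event-driven withdrawal. The same loss may reach the primary analysis for withdrawn patients who remain in the PP; the SAP leaves this open.

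The size cannot be fixed from the document. In the assumed trial of 97 per arm, two such antiplatelet patients lower the upper limit by about 1.9 points if dropped (13.07 − 11.22 = 1.85), and one lowers it by about 0.9 (11.93 − 11.00 = 0.93). Losses in the anticoagulant arm raise it instead. All of this rests on assumed counts and weights of 1. If nobody withdrew after an event, the rule turns no observed event into a missing value.

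**What to change.** Replace the sentence in section 2 with wording such as:

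> In the FAS and the PP, data collected up to the date of consent withdrawal are used as far as the patient's consent permits, and any endpoint event before that date counts. Only later information is missing. Patients whose post-baseline data may not be used are reported by arm.

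This also settles whether the rule applies in the PP. Analyses 1 and 2 and the weights of section 5.2 can stay as they are; they would apply only to endpoints that are truly unknown. The cost is a change of SAP wording and a check of what each withdrawn patient agreed to. If consent rules out any use of post-baseline data, the SAP should say so, and the count by arm is then the least the reader needs.

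### SAP section 3 tabulates FAS baseline data by treatment received, whereas section 2 and sensitivity analysis 2 analyze the FAS by allocated treatment

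*SAP*

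**What the plan says.** Section 3 names two sets: "Demographics and relevant baseline variables will be summarized for the PP and the FAS set". It then gives one grouping rule for both, without an exception: "All summaries will be broken down by the treatment patients received".

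Section 2 defines the FAS by randomization alone; it "consists of all patients that were randomized". Its grouping rule is: "According to the intention-to-treat principle, each patient will be analyzed according to the treatment she/he was randomly allocated to". Sensitivity analysis 2 in section 4.5 repeats that rule when the primary comparison is rerun on the FAS. Section 2 also brings baseline data within the FAS analysis: "Patients who withdrew their consent during the course of the study will be analyzed in the FAS including only their baseline data".

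For the PP, section 2 gives a different rule: "Each patient will be analyzed according to the treatment she/he received until follow-up visit 2". Section 4.3 places the primary analysis on the PP.

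**The concern.** Section 3 applies to the FAS a rule that section 2 reserves for the PP. A programmer cannot follow both sections for a randomized patient whose treatment differed from the allocation.

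A FAS baseline table by allocated arm is where a reader checks what randomization produced before anyone is excluded. That check matters here. The trial is open label, so a change of treatment may depend on prognosis, and the primary analysis set excludes patients for reasons that arise after randomization. Regrouped by treatment taken, the table mixes the result of randomization with later treatment choices. An imbalance in, say, arterial occlusion or NIHSS could come from either, and a real imbalance between the randomized arms could be hidden.

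The SAP itself cares about this. The footnote on missing baseline bleed imaging gives priority to preserving the randomization, and sensitivity analysis 4 examines what is lost when PP exclusions break it. No section provides a FAS baseline table by allocated arm as well.

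**Working it through.** No figure in the SAP bears on this point and none has to be recomputed. The check sets the grouping rules side by side and then asks which patients they separate.

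| Set | Baseline grouping (section 3) | Analysis grouping (section 2; 4.5 for the FAS) | Agree? |
|---|---|---|---|
| PP | treatment received | treatment received until follow-up visit 2 | yes |
| FAS | treatment received | allocated treatment | no |

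**Can received and allocated treatment differ in the FAS?** Yes. Section 2 lists as a major deviation "switching between treatment groups (cross-over) or discontinuation of the allocated treatment before follow-up visit 2 for any reason other than" a reaction to a primary outcome event or an SAE. Such patients leave the PP but stay in the FAS, so the FAS is the set in which the two groupings diverge most.

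**Where does each type of FAS patient go?**

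- Took only the allocated treatment, including those who later stopped without switching: same column under both rules.
- Took only the other arm's treatment from the start: received column differs from allocated column.
- Never started either treatment: a place under allocation, no column under section 3.
- Started as allocated, then switched: not determined. If the first treatment counts, the patient stays in the allocated column. If the last or longest counts, the patient may move. Section 3 does not choose, and it omits the time limit (until follow-up visit 2) that section 2 sets for the PP.
- Withdrew consent: section 2 keeps baseline data only. For these patients the baseline summary is all the analysis there is, and the two sections name different grouping variables for it.

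The groupings coincide if every randomized patient took only the allocated treatment. Otherwise the FAS baseline columns may differ, in size and content, from the groups in sensitivity analysis 2.

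**The case against.** The strongest reply is that section 2 already settles the matter. It gives the rule specific to the FAS and counts baseline data as part of the FAS analysis, so section 3 can be read as loose wording that the set definition overrides. That is a plausible account of how the sentence arose. It does not remove the conflict: section 3 names the FAS, says all summaries, and is where a programmer looks for the layout of the baseline table.

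The second reply is that little depends on it. This stands. The primary analysis and the modelled secondary endpoints are on the PP, and only a descriptive table is affected.

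Three stronger readings are tempting, and the document does not support them:

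- A reader might infer that every patient who crossed over lands in the wrong column. Because treatment received is undefined for switchers, this follows only under some definitions.
- A reader might try to size the shift in denominators. The SAP gives no cross-over or non-start count, so any such figure would be invented.
- A reader might extend the point to the FAS summaries of secondary endpoints in section 5.1. That section states no grouping by treatment received, and the sentence in section 3 stands under baseline characteristics, so section 2's allocation rule already covers them.

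**Conclusion.** The contradiction is real and should be corrected. As written, section 3 yields a FAS baseline table that may not describe the groups compared on the FAS and, where treatment received departs from allocation, cannot serve as a check on randomization.

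Its size is modest. It touches the FAS baseline table that accompanies sensitivity analysis 2. It leaves the primary estimate, its confidence interval, the weights and the non-inferiority conclusion unchanged. How many patients are affected depends on cross-overs and non-starters, which the SAP does not report, and on a definition of treatment received that section 3 does not give. The conclusion rests on taking section 3's wording at face value and on the absence of any other FAS baseline table in the SAP.

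**What to change.** In section 3, replace the grouping sentence with: 'FAS summaries will be broken down by allocated treatment, PP summaries by treatment received until follow-up visit 2.'

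This aligns section 3 with section 2 for both sets, gives every randomized patient a column in the FAS table, and restores the time limit for the PP. It costs one sentence under the SAP's version control and one changed grouping variable in the table code. It needs no new data and changes no analysis of an endpoint.
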